5.4.6.3 Adverse Events Occurring Secondary to Other Events

In general, adverse events occurring secondary to other events (e.g., cascade events or clinical sequelae) should be identified by their primary cause, with the exception of severe or serious secondary events. A medically significant secondary adverse event that is separated in time from the initiating event should be recorded as an independent event on the Adverse Event eCRF. For example:

- If vomiting results in mild dehydration with no additional treatment in a healthy adult, only vomiting should be reported on the eCRF.
- If vomiting results in severe dehydration, both events should be reported separately on the eCRF.
- If a severe GI hemorrhage leads to renal failure, both events should be reported separately on the eCRF.
- If dizziness leads to a fall and subsequent fracture, all three events should be reported separately on the eCRF.
- If neutropenia is accompanied by an infection, both events should be reported separately on the eCRF.

All adverse events should be recorded separately on the Adverse Event eCRF if it is unclear as to whether the events are associated.

5.4.6.4 Persistent or Recurrent Adverse Events

A persistent adverse event is one that extends continuously, without resolution, between patient evaluation timepoints. Such events should only be recorded once on the Adverse Event eCRF. The initial severity (intensity or grade) of the event will be recorded at the time the event is first reported in this study. For adverse events ongoing from the parent study, the current intensity of the event at this study start will be recorded as the initial intensity for the event in this study. If a persistent adverse event becomes more severe, the most extreme severity should also be recorded on the Adverse Event eCRF. If the event becomes serious, it should be reported to the Sponsor immediately (i.e., no more than 24 hours after learning that the event became serious; see Section 5.5.2 for reporting instructions). The Adverse Event eCRF should be updated by changing the event from "non-serious" to "serious," providing the date that the event became serious, and completing all data fields related to serious adverse events.

A recurrent adverse event is one that resolves between patient evaluation timepoints and subsequently recurs. Each recurrence of an adverse event should be recorded as a separate event on the Adverse Event eCRF.

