2.2 OTHER SAFETY OBJECTIVES

The other safety objectives for this study are as follows:

Part 1 (OLE)

- To evaluate the incidence, rate per subject-year, and severity of infection-related adverse events
- To evaluate the incidence and rate per subject-year of malignancies
- To evaluate the incidence and severity of hypersensitivity reactions
- To evaluate the incidence and the clinical significance of anti-therapeutic antibodies (ATAs)

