4.5.2 Discontinuation from Study Drug

Part 1 (OLE)

Patients must permanently discontinue study drug if they experience any of the following:

- Pregnancy
- Anaphylaxis or other severe hypersensitivity reaction
- Confirmed PML
- Develop colonic mucosal dysplasia
- Malignancy (with the exception of local and resected basal or squamous cell carcinoma of the skin), or who develop AIS, HSIL, or CIN of Grade > 1 on cervical Pap smear.
- Any patient who experiences a de novo or reactivated serious viral infection, such as HBV, HCV, HIV
- Develop life-threatening infections during the study
- Use of any prohibited medication as a concomitant therapy (see Section [4.3.2](#))

Every effort should be made to obtain information about patients who discontinue early from the study. Patients who discontinue study drug prematurely for the reasons listed above will be asked to return to the clinic for an early withdrawal from treatment visit (see Section [4.4.3](#)) and will undergo follow-up assessments for 12 weeks within Part 1

(OLE) of this study. Patients should then enter Part 2 (SM) for 92 weeks of monitoring for PML (see Section 4.4.5). The primary reason for premature study drug discontinuation should be documented on the Study Completion/Early Discontinuation eCRF.

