6.3.1 Adverse Events

Verbatim descriptions of treatment-emergent adverse events will be coded and their incidence and observation time-adjusted rate will be summarized, as appropriate. A treatment-emergent adverse event is defined as any new adverse event reported or any worsening of an existing condition on or after the first dose of study drug. In addition, separate summaries will be generated for serious adverse events, deaths, and adverse events leading to discontinuation of etrolizumab.

Analyses will also be performed for:

- Systemic hypersensitivity events

Specific analyses will be performed for anaphylactic reactions using both the anaphylactic reaction MedDRA SMQ and Sampson's criteria (see [Appendix 10 Clinical Criteria for Diagnosing Anaphylaxis](#)).

- Serious infections, in particular GI infections
- Opportunistic infections
- Malignancies
- Injection-site reactions

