1.3.2 Safety Outcome Measures

The safety outcome measures for GA29145 Part 1 (OLE) of this study are as follows:

- Incidence and severity of adverse events
- Incidence of serious adverse events
- Incidence, rate per subject-year, and severity of infection-related adverse events
- Incidence of serious infection-related adverse events
- Incidence and severity of injection-site reactions
- Incidence of adverse events leading to etrolizumab discontinuation
- Incidence of laboratory abnormalities
- Incidence and rate per subject-year of malignancies
- Incidence and severity of hypersensitivity reactions

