Summary tables will be generated for AEs, serious adverse events (SAEs), deaths, AEs leading to discontinuation of study drug, and AESIs. A listing will be generated for AEs, deaths, selected AESIs/specific AEs, and COVID-19 AEs. Pregnancies will be reported as narratives in the study CSR.

Summary tables of AEs will summarize the incidence of treatment-emergent AEs only. Treatment-emergent events are defined as any new AE reported on or after the first dose of OLE study drug or any worsening of an existing condition. Note that worsening of existing conditions include AEs ongoing from the parent study, GA29144. Otherwise, only AEs reported on or after the first dose of OLE study drug are included. If the onset date of the AE is prior to the day of first dose, the AE will be considered treatment emergent only if the most extreme intensity is greater than the initial intensity (i.e., the intensity for a given AE increases and its end date is on or after the date of the first dose). For all summary tables, the AEs will be sorted by SOC (in decreasing order of overall incidence) and then by preferred term (PT) (in decreasing order of overall incidence).

For OLE etrolizumab treatment, the incidence count for each AE PT will be defined as the number of patients reporting at least one treatment-emergent occurrence of the event (multiple occurrences of the same AE in 1 patient will be counted only once). The proportion of patients with an AE will be calculated as the incidence count divided by the total number of patients in the population. Each table will also present the total number of AEs reported where multiple occurrences of the same AE in an individual are counted separately.

Rate tables will be generated for selected AEs of interest. The rate per 100 patient years and 95% CIs will be summarized by treatment group and will be calculated by:

$$AE \text{ Rate (per 100 patient years)} = \frac{\text{Total number of AEs (in OLE only)}}{\text{Total number of patient years at risk (in OLE only)}} \times 100$$

where the total patient-years at risk is the sum over all patients of the time intervals (in years) from the first dose of study treatment in Part 1 (OLE) until the patient completes/withdraws from the study (including the 12-week safety follow-up, if applicable). Only treatment emergent AEs with an onset date after the first dose of open label Etolizumab in GA29145 will be included within these outputs.

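### The SAP's only rate rule counts adverse event records, so repeat skin carcinomas in a few patients can raise the malignancy rate and make a simple 95% CI too narrow

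*Protocol*

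**What the plan says.** Protocol 2.2 sets the objective: "To evaluate the incidence and rate per subject-year of malignancies". SAP 1.3.2 repeats it as a safety outcome measure, "Incidence and rate per subject-year of malignancies", and SAP 4 commits to reporting every safety outcome measure in the synoptic CSR. Protocol 6.3.1 says of treatment-emergent adverse events that "their incidence and observation time-adjusted rate will be summarized, as appropriate".

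SAP 4.2.2 gives the only rate rule:
- **Scope:** "Rate tables will be generated for selected AEs of interest". The selected events are not listed.
- **Numerator:** "Total number of AEs (in OLE only". This counts events, not patients.
- **Denominator:** "where the total patient-years at risk is the sum over all patients of the time intervals (in years". It runs from first OLE dose to completion or withdrawal, including the 12-week follow-up, and does not stop at a first event.
- **Interval:** a 95% CI is promised and no method is named.

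Two protocol rules feed the numerator. Under 5.4.6.4, "Each recurrence of an adverse event should be recorded as a separate event on the Adverse Event eCRF", while an event that persists without resolving is entered once. Section 4.5.2 lists among the reasons for permanent discontinuation "Malignancy (with the exception of local and resected basal or squamous cell carcinoma of the skin", so the excepted skin carcinomas do not end treatment and other malignancies do.

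SAP 4.2.2 lists Malignancies as a single category. It leaves the content to eCRF tick boxes or MedDRA groupings and does not say whether skin carcinoma is included. SAP 5 states that there is no supporting document.

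**The concern.** Malignancies are usually few in a study of this kind, so a handful of extra records can move the rate. Patients do not have equal opportunity to add records. A patient with an excepted skin carcinoma can remain on drug and under observation, and each later carcinoma after the first has resolved becomes a new record. A patient with another malignancy stops drug, completes 12 weeks of follow-up and leaves Part 1, with little time to add a second. An event rate therefore tends to give extra weight to the excepted group.

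Two things are at stake for a named safety objective. A reader cannot tell from the rate whether it reflects many patients or a few with repeat lesions. And if the unnamed interval is an ordinary Poisson interval on events, it claims more precision than the data hold.

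**Working it through.** The documents give no malignancy count, total patient-years or expected rate, so there is no plan figure to reproduce. All counts below are assumptions used to apply the SAP formula, and they take skin carcinoma to be inside the category.

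**1. Separating repeat counting from definition.** Assume 1500 patient-years and 8 patients with one other cancer each. The rate without skin carcinoma is 8/1500 × 100 = 0.53 per 100 patient-years (exact Poisson 95% CI 0.23–1.05). Add skin carcinoma in three ways:

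| Skin carcinoma patients × events each | Events | Patients | SAP event rate | Patient rate | Events ÷ patients | Patients ÷ 8 | Events ÷ 8 |
|---|---|---|---|---|---|---|---|
| 4 × 1 | 12 | 12 | 0.80 | 0.80 | 1.0 | 1.5 | 1.5 |
| 6 × 2 | 20 | 14 | 1.33 (0.81–2.06) | 0.93 | 1.43 | 1.75 | 2.5 |
| 8 × 3 | 32 | 16 | 2.13 | 1.07 | 2.0 | 2.0 | 4.0 |

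Rates are per 100 patient-years on the same 1500 patient-years. Censoring at first event would shorten the denominator slightly. The last column is the product of the two before it: 1.0 × 1.5 = 1.5, 1.43 × 1.75 = 2.5 and 2.0 × 2.0 = 4.0. Repeat counting accounts for a factor of 1.0 to 2.0. The remaining factor of 1.5 to 2.0 comes only from whether skin carcinoma is in the category.

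**2. Fewer patients, more lesions.** Assume 2000 patient-years, 6 other cancers, and 3 skin carcinoma patients with 4 events each.
- SAP event rate: (6 + 12)/2000 × 100 = 0.90 (0.53–1.42).
- Patient rate: 9/2000 × 100 = 0.45 (0.21–0.85).
- Excluding skin carcinoma: 6/2000 × 100 = 0.30 (0.11–0.65).

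Three of 9 patients supply 12 of 18 events (67%), and the event rate is 18/9 = 2.0 times the patient rate. With 2 patients × 4 events the ratio is 14/8 = 1.75. With 3 × 6 it is 24/9 = 2.67. With one event each it is 1.0. These ratios do not depend on patient-years.

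**3. Interval.** Let other cancers be Poisson with mean 6, skin carcinoma patients Poisson with mean 3, and events per such patient 1 + Poisson(m − 1). The mean event count is 6 + 3m. The variance is 6 + 3(m² + m − 1). At m = 4 that is 63 against a mean of 18, a ratio of 3.5, where a Poisson interval assumes 1. In 200,000 simulated trials, coverage of a nominal 95% exact Poisson interval on events was:

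| Mean events per skin carcinoma patient (m) | Coverage |
|---|---|
| 1 | 95.7% |
| 2 | 87.9% |
| 4 | 74.5% |
| 6 | 61.2% |

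**The case against.** The best reply is that most of what a reader needs is already planned. The objective has two halves, and incidence is patient-based in SAP 4.2.2: repeats of the same event in one patient count once. The same section puts total event counts beside patient counts, sorts tables by preferred term so that skin carcinoma terms get their own rows, and plans listings in which repeat lesions would show. The study is single-arm with no hypothesis tests, Part 1 was ended by the sponsor, and the documents tie no decision rule to this rate. All of that stands. It limits the point to the rate, for which neither a first-event version nor a split by type is planned.

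Three stronger readings are tempting but not supported:
- **That the plan pools skin carcinoma with all other cancers.** This is the default reading of a single category, but no text says so. The content of the category is simply not fixed.
- **That repeat lesions inflate the rate 1.5 to 4 times.** In the first table that range mixes a change of definition with repeat counting, and the 1.5-fold case contains no repeats.
- **That a safety rate must match the discontinuation rule.** Nothing requires this. Section 4.5.2 itself treats these carcinomas as malignancies with an exception, and the protocol gives no numerical background rate for comparison.

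The recurrence sentence in 5.4.6.4 is also only a recording rule. The operative text is the formula in SAP 4.2.2.

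**Conclusion.** The point holds for the rate. The formula counts events without a first-event limit, it is the only rule given for a rate that must be reported, and the protocol lets one group of patients stay in the study and add records. A few patients with repeat skin carcinomas could therefore raise the rate, and a 95% CI that treats events as independent would be too narrow.

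The size cannot be known from the documents. On the first set of illustrative counts, repeat counting alone gives a factor of 1.0 to 2.0. With fewer patients and up to 6 lesions each it reaches 2.67, and with one event per patient it vanishes. The coverage loss depends on the assumed clustering and on a Poisson method that the SAP does not name. Everything is conditional on skin carcinoma being counted under Malignancies, which the SAP leaves open. This is an inexpensive improvement to reporting and does not affect the patient-based incidence.

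**What to change.** In SAP 4.2.2:

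1. State the MedDRA search or eCRF field that defines Malignancies, and list malignancies among the events that get a rate table.
2. Keep the event rate. Name its interval method and, if it treats events as independent, say so.
3. Add patients with a first malignancy per 100 patient-years, with time censored at that first event, for (a) all malignancies, (b) malignancies excluding basal and squamous cell skin carcinoma by preferred term, and (c) basal and squamous cell skin carcinoma. Splitting by preferred term keeps (b) and (c) from overlapping and avoids relying on local or resected status, which the documents do not say is coded. A patient with both kinds counts once in each row, so (b) and (c) need not sum to (a).
4. Use exact Poisson intervals for the first-event rates.
5. List adenocarcinoma in situ, HSIL, CIN of Grade >1 and colonic dysplasia separately, since Protocol 4.5.2 names them alongside malignancy.

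This uses adverse event data already collected and changes no clinical rule. The cost is SAP wording and a few table rows. Each added rate rests on fewer events, so its interval will be wider.

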5.4.6.5 Abnormal Laboratory Values

Not every laboratory abnormality qualifies as an adverse event. A laboratory test result must be reported as an adverse event if it meets any of the following criteria:

- Is accompanied by clinical symptoms
- Results in a change in study treatment (e.g., dosage modification, treatment interruption, or treatment discontinuation)
- Results in a medical intervention (e.g., potassium supplementation for hypokalemia) or a change in concomitant therapy
- Is clinically significant in the investigator's judgment

It is the investigator's responsibility to review all laboratory findings. Medical and scientific judgment should be exercised in deciding whether an isolated laboratory abnormality should be classified as an adverse event.

If a clinically significant laboratory abnormality is a sign of a disease or syndrome (e.g., alkaline phosphatase and bilirubin 5× upper limit of normal [ULN] associated with cholestasis), only the diagnosis (i.e., cholestasis) should be recorded on the Adverse Event eCRF.

If a clinically significant laboratory abnormality is not a sign of a disease or syndrome, the abnormality itself should be recorded on the Adverse Event eCRF, along with a descriptor indicating if the test result is above or below the normal range (e.g., "elevated potassium," as opposed to "abnormal potassium"). If the laboratory abnormality can be characterized by a precise clinical term per standard definitions, the clinical term should be recorded as the adverse event. For example, an elevated serum potassium level of 7.0 mEq/L should be recorded as "hyperkalemia."

Observations of the same clinically significant laboratory abnormality from visit to visit should not be repeatedly recorded on the Adverse Event eCRF, unless the etiology changes. The initial severity of the event should be recorded, and the severity or seriousness should be updated any time the event worsens (see Section 5.4.6.4 for more details).

5.4.6.6 Abnormal Vital Sign Values

Not every vital sign abnormality qualifies as an adverse event. A vital sign result must be reported as an adverse event if it meets any of the following criteria:

- Is accompanied by clinical symptoms
- Results in a change in study treatment (e.g., dosage modification, treatment interruption, or treatment discontinuation)
- Results in a medical intervention or a change in concomitant therapy
- Is clinically significant in the investigator's judgment

It is the investigator's responsibility to review all vital sign findings. Medical and scientific judgment should be exercised in deciding whether an isolated vital sign abnormality should be classified as an adverse event.

If a clinically significant vital sign abnormality is a sign of a disease or syndrome (e.g., high blood pressure), only the diagnosis (i.e., hypertension) should be recorded on the Adverse Event eCRF.

Observations of the same clinically significant vital sign abnormality from visit to visit should not be repeatedly recorded on the Adverse Event eCRF, unless the etiology changes. The initial severity of the event should be recorded, and the severity or seriousness should be updated any time the event worsens (see Section 5.4.6.4 for more details).

5.4.6.7 Abnormal Liver Function Tests

The finding of an elevated ALT or AST ($>3 \times \text{ULN}$) in combination with either an elevated total bilirubin ($>2 \times \text{ULN}$) or clinical jaundice in the absence of cholestasis or other causes of hyperbilirubinemia is considered to be an indicator of severe liver injury (as defined by Hy's law). Therefore, investigators must report as an adverse event the occurrence of either of the following:

- Treatment-emergent ALT or AST $>3 \times \text{ULN}$ in combination with total bilirubin $>2 \times \text{ULN}$
- Treatment-emergent ALT or AST $>3 \times \text{ULN}$ in combination with clinical jaundice

The most appropriate diagnosis or (if a diagnosis cannot be established) the abnormal laboratory values should be recorded on the Adverse Event eCRF (see Section 5.4.6.5) and reported to the Sponsor immediately (i.e., no more than 24 hours after learning of the event), either as a serious adverse event or an adverse event of special interest (see Section 5.5.2).

5.4.6.8 Deaths

Part 1 OLE (including the 12-week safety follow-up period)

All deaths that occur during the protocol-specified adverse event reporting period (see Section 5.4.1), regardless of relationship to study drug, must be recorded on the Adverse Event eCRF and immediately reported to the Sponsor (see Section 5.5.2). This includes death attributed to progression of CD.

Death should be considered an outcome and not a distinct event. The event or condition that caused or contributed to the fatal outcome should be recorded as the single medical concept on the Adverse Event eCRF. Generally, only one such event should be reported. If the cause of death is unknown and cannot be ascertained at the time of reporting, "**unexplained death**" should be recorded on the Adverse Event eCRF. If the cause of death later becomes available (e.g., after autopsy), "unexplained death" should

be replaced by the established cause of death. The term "**sudden death**" should not be used unless combined with the presumed cause of death (e.g., "sudden cardiac death").

If the death is attributed to progression of CD, "Crohn's disease progression" should be recorded on the Adverse Event eCRF.

Part 2 (SM)

During the 92-week safety monitoring for PML, all deaths due to PML, regardless of relationship to study drug, must be reported to the sponsor as a serious adverse event on the Adverse Event eCRF (see Section 5.4.6).

If the investigator is made aware of a non-PML event of death, then it should be reported directly to Roche or its designee either by faxing or by scanning and e-mailing the Serious Adverse Event/Adverse Event of Special Interest Reporting Form using the fax number or e-mail address provided to investigators.

5.4.6.9 Preexisting Medical Conditions

Past resolved adverse events will be recorded in the medical history according to their medical relevance. Adverse events reported ongoing at the end of Study GA29144 will be stated unresolved in those studies and also reported in Study GA29145.

A preexisting medical condition should be recorded as an adverse event only if the frequency, severity, or character of the condition worsens during the study. When recording such events on the Adverse Event eCRF, it is important to convey the concept that the preexisting condition has changed by including applicable descriptors (e.g., "more frequent headaches").

5.4.6.10 Lack of Efficacy or Worsening of Crohn's Disease

Medical occurrences or symptoms of deterioration that are anticipated as part of CD should be recorded as an adverse event if judged by the investigator to have unexpectedly worsened in severity or frequency or changed in nature at any time during the study. When recording an unanticipated worsening CD on the Adverse Event eCRF, it is important to convey the concept that the condition has changed by including applicable descriptors (e.g., "accelerated Crohn's disease" or "worsening of Crohn's disease").

